16.1 Ethics committee, Institutional Review Board and regulatory authorities

The CIP and/or other relevant documents are submitted to the appropriate EC/IRB and regulatory authorities. This clinical investigation will not begin until the required approval from the EC/IRB and regulatory authorities have been obtained. Any amendment to the protocol will be submitted to the same EC/IRB and regulatory authority.

16.4 Financial conditions

Coloplast A/S will compensate all investigators involved in the clinical investigation for their time and resources spent on the investigation. All financial agreements with the investigation sites involved in the clinical investigation will be specified in a sponsor investigator agreement.

17 Informed consent process

Written informed consent is obtained from all subjects participating in the investigation after thorough written and verbal information. The information is given by the investigator or his/her representative in the subjects' native non-technical language. Each subject will be fully informed about the aim of the investigation, procedures, potential risks or inconveniences and/or expected benefits, all anticipated adverse device effects and then have a minimum of 24h (ensure ample time) before deciding on participation. The subjects will be informed that their participation is voluntary and that they may leave the investigation at any time, without this having any influence on their further treatment.

The informed consent signature form includes personally dated signatures of the subject and the PI or his/her representative responsible for conducting the informed consent process. A copy will be provided to the subject.

If new information is to be given during the investigation, sponsor will inform the investigators, and the new information is given to the subjects by the investigator. If new information becomes available that can significantly affect a subject's future health and medical care that information will be provided to the subject in written form. CM is responsible for writing the information and providing the approved Subject Information and Consent Form to investigators that will further provide it to the subjects. If applicable, all affected subjects shall be asked to confirm their continuing informed consent in writing.

This procedure also applies to informed consent obtained from a subject's legal representative. The procedure cannot waive the subjects' legal rights.

18 Subject compensation

18.1 Compensation in case of injury

Product liability and No-Fault Clinical Investigation Insurance covering the duration of the clinical investigation are in place, to enable compensation in the event of an injury to a participating subject.

18.2 Compensation for participating in the clinical investigation

Subjects will be compensated with a voucher per visit, paid by Coloplast A/S with the value as described below:

	Subjects
Visit 0 (V0)	-
Visit 1 (V1)	[REDACTED]
Visit 2 (V2)	[REDACTED]

This is to compensate for any inconvenience caused during the catheterisations, time used. Travel expenses will be accounted for separately. For Danish subjects, the remuneration/vouchers are taxable (B-income) and it is the responsibility of the subject to declare this to SKAT.

19 Adverse events, adverse device effects and device deficiencies

19.1 Adverse events

An adverse event is any untoward medical occurrence, unintended disease or injury, or untoward clinical signs (including abnormal laboratory findings) in subjects, whether or not related to the investigational medical device(s) or the comparator(s), or the procedures involved. The adverse event shall be marked with the intensity mild, moderate or severe. This could include events such as headache or dizziness.

19.4.3 Unanticipated serious adverse device effect (USADE)

An unanticipated serious adverse device effect is a serious adverse device effect which by its nature, incidence, severity or outcome has not been identified in the current version of the risk analysis report.

19.5 Medical care of subjects

Principal investigator shall ensure that adequate medical care is provided, during and after participation in the clinical investigation, to a subject experiencing an adverse event. All ongoing ADEs, SAEs, SADEs and DDs that could have led to a SAE at subject termination will be followed according to the Risk Benefit analysis (see 8.2). An ongoing adverse event at subject termination visit is documented as the current status for the adverse event and will not be followed up.

The subjects shall be informed of any new significant findings occurring during the clinical investigation, including the need for additional medical care that can be required, and of the nature and possible cause of any adverse events experienced.

19.6 Reporting and timelines

19.7 Investigator's reporting responsibilities

- PI at each site must assess all (S)AE's that occur at his/her site.
- All serious adverse events and serious adverse device effects must be reported to sponsor within 24 hours of the site becoming aware of the event.
- A device deficiency that could have led to a serious adverse event but did not because suitable action was taken, intervention had been made or because of fortunate circumstances should be reported to sponsor within 24 hours of the site becoming aware of the event.
- New findings and/or updates in relation to already reported serious events should also be reported to sponsor within 24 hours of the site becoming aware of the event.
- Device deficiencies and all adverse device effects related to investigational product and/or comparator must be reported to sponsor within 24 hours of becoming aware of the event.

When reporting the SAE, the relationship to the test material shall be described whether the event is considered

- **Not related**, the event has no temporal relationship with the use of the test material or the procedures.
- **Unlikely related**, the relationship with the use of the test material seems not relevant and/or the event can be reasonably explained by another cause, but additional information may be obtained.
- **Possible related**, the relationship with the use of the test material is weak but cannot be ruled out completely. Alternative causes are also possible (e.g. an underlying or concurrent illness/ clinical condition or/and an effect of another device, drug or treatment). Cases were relatedness cannot be assessed or no information has been obtained should also be classified as possible.
- **Probable related**, the relationship with the use of the test material seems relevant and/or the event cannot reasonably be explained by another cause, but additional information may be obtained.
- **Definitely related/Causal relationship**, the event has a temporal relationship with the test material use/application or procedures.

and the intensity of the event should be considered, as such:

- **Mild**, the intensity of the event is mild with no further action or intervention
- **Moderate**, the intensity of the event will lead to an action or intervention to solve the event
- **Severe**, the intensity of the event will lead to follow up on the action or intervention, as the effect of the action or intervention may not decrease the symptoms.

All above events must be reported by use of the relevant adverse event/serious adverse event/device deficiency form.

The investigation will be registered in a publicly accessible database before recruitment of the first subject. The results of the investigation, positive as well as inconclusive and negative will be published in the same publicly accessible database. The subjects' identity will remain confidential. Publication of results in the database will be conducted per the law of personal data protection and will be initiated as soon as scientifically acceptable, however, within one year after the last subject has completed the investigation. Data from the investigation is considered confidential until it is published per the conditions of this Clinical Investigation Plan and the 'Clinical Publication Policy'. Sponsor may publish anonymous single subject case stories (or public, if the subject consents) at any time during and after the investigation. The identification of the participant must not be possible. Sponsor reserves the right to use the data (published and unpublished) for reimbursement or regulatory purposes.

23 Suspension/termination of the clinical investigation

Sponsor will withdraw from sponsorship of the clinical investigation if

- major non-adherence to the clinical investigation plan is occurring
- it is anticipated that the subject recruitment will not be adequate to meet the investigation objectives (at least 75% of the subjects should be entered within the recruitment time).

In case sponsor withdraws, sponsorship for the subjects already recruited into the clinical investigation will continue.

24 Bibliography

Averbeck, M. A., Krassioukov, A., Thiruchelvam, N., Madersbacher, H., Bøgelund, M., & Igawa, Y. (2018). The impact of different scenarios for intermittent bladder catheterization on health state utilities: results from an internet-based time trade-off survey. *J Med Econ*, 21(10), 945-952. doi:10.1080/13696998.2018.1486846

Coloplast A/S. (2021a). Clinical Investigation Report CP322. Doc. No. VV-0332935.

Coloplast A/S. (2021b). Laboratory Report - Catheter induced bladder mucosa suction - pressure and trauma. Doc. No. VV-0352683 vs. 1.0.

Coloplast A/S. (2021c). Laboratory report_TM7078_Mucosal suction summary. Doc. No. VV-0352684 vs. 1.0.

Coloplast A/S. (2021d). Investigators Brochure CP334. Doc. No. VV-0343853

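### In section 19.7 the top causality grade for SAEs rests on timing alone, so the five grades overlap and relatedness can be misgraded

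*Combined protocol and SAP*

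**What the plan says.** Section 19.7 introduces the scale with "When reporting the SAE, the relationship to the test material shall be described whether the event is considered" and lists five grades:

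- The lowest grade, *Not related*, applies where "the event has no temporal relationship with the use of the test material or the procedures".
- The second grade, *Unlikely*, applies where "the relationship with the use of the test material seems not relevant and/or the event can be reasonably explained by another cause".
- The middle grade, *Possible*, applies where "the relationship with the use of the test material is weak but cannot be ruled out completely". Other causes may also be present. A default clause extends this grade: "Cases were relatedness cannot be assessed or no information has been obtained should also be classified as possible".
- The fourth grade, *Probable*, applies where "the relationship with the use of the test material seems relevant and/or the event cannot reasonably be explained by another cause".
- The top grade, *Definitely related/Causal relationship*, applies where "the event has a temporal relationship with the test material use/application or procedures".

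The same section says "PI at each site must assess all (S)AE's that occur at his/her site". It sets a 24-hour deadline for reporting all SAEs and SADEs to the sponsor, and the same deadline for device deficiencies and for ADEs related to either product.

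Under section 19.5, ADEs, SAEs and SADEs still ongoing at termination are followed further, whereas an ongoing adverse event is only recorded at its current status. Section 19.4.3 defines a USADE as a particular kind of SADE, so it presupposes that the event has been attributed to a device.

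**The concern.** A causality scale should run from weak to strong evidence, with each event belonging in one grade. Here the three middle grades call for judgement about relevance or about other causes, while the highest grade calls only for timing. An investigator who follows the text exactly can put an SAE with an obvious other explanation in the top grade. One who goes by the label *Causal relationship* would not. The trial is open-label and may run at up to three sites in Denmark and the USA, so the same event could be graded in two ways.

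The design makes timing a poor guide. Section 5.1 allows visit 2 on the day after visit 1, so an event at visit 2 may be close in time to the use of both devices.

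What is at stake is whether an SAE is classed as a SADE, and from there possibly as a USADE, for a device that section 4.1 says is neither CE-marked nor 510(k)-cleared. Section 9.1.3 relies on unanticipated device effects being recognised quickly.

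**Working it through.** The plan states no figure on this point and no arithmetic applies. The check is to ask what each definition requires and then try some simple cases against the wording.

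**Step 1: what each grade requires.**

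| Grade | Timing | Relevance or strength of the link | Other causes |
|---|---|---|---|
| Not related | Absent | Not mentioned | Not mentioned |
| Unlikely | Not mentioned | Seems not relevant | and/or a reasonable one exists |
| Possible | Not mentioned | Weak, not excluded (or cannot be assessed) | May exist |
| Probable | Not mentioned | Seems relevant | and/or no reasonable one |
| Definitely related | Present | Not mentioned | Not mentioned |

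**Step 2: the two ends.** *Not related* is the absence of a temporal relationship and *Definitely related* is its presence. One or the other is true of any event, so the two ends cover every case and the middle grades have no territory of their own.

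**Step 3: trial cases.**

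- *An SAE soon after catheterisation with a reasonable other explanation.* It meets *Unlikely* through the clause on other causes, and it meets *Definitely related* through timing. The two grades lie at opposite sides of the scale.
- *An SAE soon after catheterisation with a relevant link and no other explanation.* It meets *Probable* and *Definitely related*. Nothing in the text separates the two.
- *An SAE soon after catheterisation whose relatedness cannot be assessed.* The default clause sends it to *Possible*, and timing sends it to *Definitely related*.

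**Step 4: order of evidence.** Either limb of *Probable* needs a judgement beyond timing, and the top grade needs none. In terms of causal evidence, the top grade is therefore less demanding than *Probable*. A strict ranking against *Possible* cannot be claimed, because the default clause also admits events with no link in time.

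**Step 5: what depends on the grade.** All SAEs go to the sponsor within 24 hours whatever their grade, so that deadline does not move. SADE and USADE status presuppose attribution to a device and can move. For non-serious events, the 24-hour ADE deadline in 19.7 and the follow-up rule in 19.5 could also move, but only if this scale is the one used for them. The primary endpoint models, the power statement and the fixed-sequence test do not use relatedness.

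**The case against.** The strongest reply is that the full label includes *Causal relationship* and that *Unlikely* gives an explicit home to events with another explanation, so a competent investigator would grade sensibly. That may often happen. It shows that the definitions overlap, however, and relies on the reader setting aside the only sentence that defines the top grade. No other text adds a causal criterion to it. This does limit the claim: the scale *can* misgrade, not that it always will.

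Four stronger readings are tempting, and the documents do not support them.

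- *All adverse events are affected.* The scale is introduced for SAEs. Its wider use is an inference from the investigator's duty to assess all (S)AEs and from the absence of another scale in the available text. The text of section 19.2, which defines an ADE, was not available, nor was that of 19.4.1 or 19.8.
- *The speed of SAE reporting depends on the grade.* Section 19.7 says otherwise.
- *Safety tables will be distorted.* Section 10.2 says only that adverse events and device deficiencies are assessed in the safety population. No visible text plans a table by grade or says which grades count as device-related. If both *Probable* and *Definitely related* count, confusing those two changes no count; confusing *Unlikely* with *Definitely related* could.
- *Any event after a study catheterisation qualifies as definite.* The plan sets no time window for a temporal relationship, so that cannot be read from it.

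It is also fair to say that the literal error over-attributes events rather than hiding them, and that the same wording applies to both devices.

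**Conclusion.** The point holds as a defect in a stated rule. For SAEs, the scale in 19.7 is neither ordered by strength of evidence nor mutually exclusive, and it can misgrade relatedness, mainly towards over-attribution to a device. The consequence is possible misclassification of SADEs and USADEs and inconsistent grading between sites or investigators.

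Extending this to ADE classification, its 24-hour reporting and its follow-up rests on the assumption that the same scale is used for non-serious events.

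The size cannot be given as a number, because the available text states no expected event rate. With 42 subjects and two study catheterisations each (42 × 2 = 84), a single regraded event could be visible in a count of device effects, but that is true of any small study. The efficacy conclusions are not touched. The change is worth making because the defect is clear and cheap to remove.

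**What to change.** In section 19.7, reword *Definitely related/Causal relationship* so that three conditions must all hold: a temporal relationship, an event that is a plausible effect of the device or procedure, and other causes adequately ruled out. State that timing alone is not sufficient for this grade. Add that *Probable* applies when the three conditions are not all met, and check the remaining definitions so that the five grades are ordered and each event fits only one. State also whether the scale applies to all AEs or to SAEs only, and, if to SAEs only, how relatedness of non-serious events is to be judged.

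The cost is a sentence or two in the plan and a reminder in site training. No change to the sample size, endpoints or analysis is needed.
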